10.4 Contraceptive Guidance and Collection of Pregnancy Information

10.4.1 Definitions

10.4.1.1 *Highly Effective Form of Contraception (Failure Rate <1%)*

A highly effective form of contraception (failure rate of <1%) is defined as follows:

- Combined (estrogen and progestogen containing) hormonal contraception associated with inhibition of ovulation:
 - Oral
 - Intravaginal
 - Transdermal
- Progestogen-only hormonal contraception associated with inhibition of ovulation:
 - Oral
 - Injectable
 - Implantable
- Intrauterine device
- Intrauterine hormone-releasing system
- Bilateral tubal occlusion
- Vasectomized partner
- Sexual abstinence is considered a highly effective method only if defined as refraining from heterosexual intercourse during the entire period of risk associated with the trial intervention. The reliability of sexual abstinence needs to be evaluated in relation to the duration of the clinical trial and the preferred and usual lifestyle of the participant.

10.4.1.2 *Women of Childbearing Potential, Women of Nonchildbearing Potential, and Fertile Men*

A woman is considered to be a woman of childbearing potential following menarche and until becoming postmenopausal unless permanently sterile.

A woman is considered to be of nonchildbearing potential if she fulfills either of the following criteria:

- Underwent permanent sterilization including hysterectomy, bilateral oophorectomy, or bilateral salpingectomy
- Is in a postmenopausal state, which is defined as no menses for 12 consecutive months without an alternative medical cause, and confirmed with an FSH level >40 IU/mL.

A man is considered fertile after puberty unless permanently sterile by bilateral orchidectomy.

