- p. 12-lead ECG assessments will be performed after the participant has been at rest for approximately 3 minutes. At Screening, the average of 3 consecutive ECGs collected 1 to 2 minutes apart will be used to determine participant eligibility; at Baseline, only 1 reading is required for determination of eligibility. At approximately 2 hours following dosing at weekly time points, single 12-lead ECGs will be obtained. Additional ECGs can be performed at the investigator's discretion (eg, if abnormalities are noted).

- q. At Screening and Baseline, blood pressure and heart rate assessments should be performed in order to confirm eligibility (see Exclusion Criterion in [Section 5.2](#)). Triplicate supine heart rate and blood pressure measurements should be taken at approximately 1-minute intervals predose (Day 1 only, Baseline), and at approximately 2 hours after dosing on Day 1 and Weeks 1 through 6. The triplicate supine heart rate and blood pressure measurements will be followed by a single measurement after approximately 2 minutes in a standing position to allow for orthostatic assessments. Additional time points can be added at the investigator's discretion (eg, if abnormalities are noted). Further details are provided in [Section 8.2.3](#) and in the Operations Manual.
- r. The "Baseline/Screening" C-SSRS form will be completed for all participants at Screening to determine eligibility and the "Since Last Visit" C-SSRS form will be completed at Baseline to ensure that the participant continues to qualify for the trial. The "Since Last Visit" C-SSRS form will also be completed at weekly time points after Baseline.
- s. EPS assessments can be completed at any time during the trial, per investigator discretion, if symptoms are present.
- t. Prior and concomitant medications should be recorded from Screening through the participant's last visit/contact.
- u. Adverse events (serious and nonserious) should be recorded from the first dose of IMP through the participant's last visit/contact.
- v. The Week 6 prolactin results will be partially blinded; the investigator will be notified if the prolactin levels exceed a predefined limit with instructions to send the participant for appropriate follow-up.
- w. For women of childbearing potential only. Pregnancy tests can be performed at any time during the trial at the discretion of the investigator if pregnancy is suspected. Any urine pregnancy tests that are positive must be confirmed using a serum test.

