5.1 Inclusion Criteria

Individuals are eligible for participation in this trial only if all of the following criteria apply:

General	
1.	Male and female participants, ages 18 to 65 years, inclusive, at the time of signing the ICF.
Target Disease Characteristics	
2.	Primary diagnosis of schizophrenia per DSM-5, as confirmed by the MINI for Psychotic Disorders version 7.0.2.
3.	CGI-S ≥ 4 (moderately to severely ill) at the time of signing the ICF and Baseline.

4.	
PANSS Total Score between 85 and 120, inclusive, at the time of signing the ICF and at Baseline.
 
Additionally, participants must meet a score of ≥ 4 (moderate or greater) for ≥ 2 of the following Positive Scale items at the time of signing the ICF and at Baseline:
 
 • Positive Scale Item 1 (delusions) • Positive Scale Item 2 (conceptual disorganization) • Positive Scale Item 3 (hallucinatory behavior) • Positive Scale Item 6 (suspiciousness/persecution)
5.	
Experiencing an acute exacerbation or relapse of psychotic symptoms, with onset less than 60 days prior to signing the ICF.
 
 • Participant requires hospitalization for this acute exacerbation or relapse of symptoms • If participant is already an inpatient at the time of signing the ICF, has been hospitalized for ≤ 14 days for the current episode of psychosis at the time of signing the ICF, excluding hospitalization for psychosocial reasons
6.	
Scores as follows (normal to mild symptoms) at the time of signing the ICF and Baseline (Day 1):
 
 • All individual items of the SAS < 2 • All individual items (Items 1-7) of the AIMS < 2 • Clinical global assessment item of the BARS < 3
7.	
Willing to discontinue all prohibited medications to meet protocol-required washouts prior to and during the trial period.

8.	
Resides in a stable living environment as demonstrated by the ability to provide contact information for themselves and/or family/friend/caregiver.

Other and Administrative Criteria

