9.	
Agree to comply with the following contraception requirements during the trial and for 7 days after the last dose of IMP:
 
 • Sexually active men must agree to use a condom and practice contraception during treatment and until the end of relevant systemic exposure (ie, 7 days after the last dose of IMP). • Sexually active women of childbearing potential must use highly effective contraception as defined in Section 10.4.1.1 
In addition, male participants should not donate sperm for a minimum of 7 days following the last dose of IMP.

10.	
Body mass index of 18.0 to 40.0 kg/m² and a total body weight ≥ 50 kg (110 lbs).

11.	
Capable of giving signed informed consent, which includes compliance with the requirements and restrictions listed in the ICF and in Section 10.1.3.

12.	
Ability, in the opinion of the investigator, to understand the nature of the trial, participate in trial visits, and comply with protocol requirements, including the prescribed dosage regimens, scheduled visits, laboratory tests, outcomes measures, and other trial procedures.

Abbreviations: AIMS=Abnormal Involuntary Movement Scale; BARS=Barnes Akathisia Rating Scale; CGI-S=Clinical Global Impression–Severity of Symptoms; DSM-5=Diagnostic and Statistical Manual of Mental Disorders, Fifth Edition; ICF=informed consent form; IMP=investigational medicinal product; MINI=Mini International Neuropsychiatric Interview; PANSS=Positive and Negative Syndrome Scale; SAS=Simpson Angus Scale.

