10.2 Clinical Laboratory Tests

Protocol-required tests detailed in [Table 7](#) will be performed by a central laboratory, with the exception of those specified to be done locally in the Operations Manual.

Protocol-specific requirements for inclusion or exclusion of participants are detailed in [Section 5](#).

Additional tests may be performed at any time during the trial as determined necessary by the investigator or required by local regulations.

Serology (screening for human immunodeficiency virus, hepatitis B virus, hepatitis C virus) will be done at Screening.

Serum/urine pregnancy tests are required for all women of childbearing potential at the time points indicated in the Schedule of Assessments; however, pregnancy tests can be done anytime during the trial at the investigator's discretion.

Participants must have SARS-CoV-2 testing done with a negative test result prior to admission to the inpatient facility, refer to site procedures for additional details on

testing. Additional SARS-CoV-2 testing may be performed after admission per the investigator's discretion.

Table 7 Protocol-Required Safety Laboratory Tests

Laboratory Assessments	Parameters	
Hematology	Platelet count RBC count Hemoglobin Hematocrit Prothrombin time and INR MCH MCHC MCV	WBC count with differential (absolute and %): 
 • Neutrophils • Lymphocytes • Monocytes • Eosinophils • Basophils
Chemistry	BUN Creatinine Glucose Albumin Cholesterol (total, HDL, LDL) Triglycerides Uric acid Potassium Sodium Calcium Bicarbonate Chloride Magnesium Phosphorus	ALT AST Alkaline phosphatase GGT CPK Total bilirubin and direct bilirubin Total protein Glycosylated hemoglobin
Routine Urinalysis	Specific gravity pH, glucose, protein, blood, ketones, bilirubin, urobilinogen, nitrite, leukocyte esterase by dipstick	
Additional Required Protocol-specific Tests	Serum/urine pregnancy test (as needed in women of childbearing potential) CPK reflex for isoenzymes if CPK $>3 \times$ ULN; serum and urine myoglobin collected if CPK $>5 \times$ ULN Prolactin	
Other Screening Tests	A confirmatory FSH is required for post-menopausal women Breathalyzer test for alcohol and urine drug screen Serology (HIV, HBsAg, HBcAb, hepatitis C antibody) SARS-CoV-2 testing (Additional testing may be done at investigator discretion) Thyroid-stimulating hormone with reflex to free T4 if abnormal	

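### The FSH limit that confirms postmenopausal status is written in IU/mL, a unit in which it cannot realistically be met, so the postmenopausal route out of the childbearing-potential class is closed as written

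*Protocol*

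**What the plan says.** Protocol Section 10.4.1.2 treats a woman as of childbearing potential "following menarche and until becoming postmenopausal unless permanently sterile". There are two ways out of that class: "A woman is considered to be of nonchildbearing potential if she fulfills either of the following criteria". The first is permanent sterilization (hysterectomy, bilateral oophorectomy or bilateral salpingectomy). The second reads "Is in a postmenopausal state, which is defined as no menses for 12 consecutive months without an alternative medical cause, and confirmed with an FSH"; the limit is then given: "confirmed with an FSH level >40 IU/mL".

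Table 7 in Section 10.2 makes the test compulsory: "A confirmatory FSH is required for post-menopausal women".

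The class has two consequences:

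- Inclusion Criterion 9 in Section 5.1: "Sexually active women of childbearing potential must use highly effective contraception as defined in Section 10.4.1.1".
- The serum and urine pregnancy tests in the Schedule of Assessments (Section 1.3), whose footnote says "For women of childbearing potential only".

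Postmenopausal women are within the age range, since Inclusion Criterion 1 reads "Male and female participants, ages 18 to 65 years, inclusive, at the time of signing the ICF".

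The FSH limit appears only once in the two documents. Nothing else gives a different cut-off, a different unit or an exception to the test.

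**The concern.** The number 40 is plausible as an FSH limit in mIU/mL or IU/L, which are the same unit. In IU/mL it is a thousand times larger. FSH confirmation is joined to the 12-month condition by a plain conjunction, so amenorrhea alone is not enough. The default class is childbearing potential, so a woman who cannot meet the FSH condition stays there.

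This is an operative threshold and not background text. The test is mandatory, and its result decides whether the contraception criterion and the pregnancy tests apply. Section 8 of the protocol allows no waivers or exemptions, so a site has no formal way to set the literal limit aside. At stake are an eligibility definition that cannot be satisfied as written, unneeded tests, possible screen failures under Inclusion Criterion 9, and inconsistent classification if some sites read the limit literally and others do not.

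**Working it through.** The limit is a stated threshold and not a derived figure, so the plan offers no calculation to reproduce. The check is a unit conversion followed by a reading of the rule.

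**Step 1: convert the limit.** Input: more than 40 IU/mL (Protocol Section 10.4.1.2).

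40 IU/mL × 1000 mL/L = 40,000 IU/L = 40,000 mIU/mL.

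**Step 2: compare with FSH values.** The documents give no reference range, so the values below are an assumption, deliberately wide. The ratio is 40,000 divided by the value in IU/L.

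| Assumed FSH (IU/L) | Same value (IU/mL) | Above 40 IU/mL? | Limit ÷ value |
|---|---|---|---|
| 25 | 0.025 | No | 1600 |
| 50 | 0.05 | No | 800 |
| 100 | 0.10 | No | 400 |
| 150 | 0.15 | No | 267 |
| 200 | 0.20 | No | 200 |

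The result is not sensitive to the assumption. A value ten times the top of the range, 2000 IU/L, is 2 IU/mL and still 40 ÷ 2 = 20 times below the limit.

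**Step 3: compare with cut-offs.** Again by assumption, for cut-offs of 25, 30 and 40 IU/L the written limit is 1600, 1333 and 1000 times higher. If the number 40 is kept and only the unit changes to mIU/mL, the factor is exactly 1000.

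**Step 4: follow the rule for each woman.**

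- *Permanently sterilized:* she qualifies by the first route, and FSH plays no part.
- *Not sterilized, 12 months without menses:* she needs the FSH confirmation, cannot meet it, and stays in the childbearing-potential class. She has a serum pregnancy test at Screening and urine tests at Baseline and at Week 6 or early termination.
- *As above, and sexually active:* she must also use a method listed in Section 10.4.1.1. The list includes hormonal and intrauterine methods, bilateral tubal occlusion, a vasectomized partner and, under conditions, abstinence. Only if she uses none of them does she fail Inclusion Criterion 9.

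**Step 5: look for an effect on the analysis.** The primary model (SAP Section 5.9.2) uses treatment, geographic region, visit, the treatment-by-visit interaction and the baseline score. Fertility status is not in it. It appears in SAP Section 5.6 as one descriptive baseline item. The sample size (Protocol Section 9.5) does not use it either.

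**The case against.** The strongest reply is that this is a slip in a unit that nobody would apply. A laboratory that reports in mIU/mL or IU/L would probably have 40 applied in its own unit, and then no woman would be misclassified. The documents contain no second FSH figure that contradicts the first, and the claim that the limit cannot be met rests on an assumed range. The error is also in the safe direction: no woman of childbearing potential is released from contraception or testing. Participants are inpatients through Week 6 or early termination, and the contraception requirement ends 7 days after the last dose.

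Most of this stands, and it limits the consequence. It does not rescue the text. The assumed range can be stretched tenfold without changing the result, and a site that quietly applies 40 in another unit is departing from the protocol without a record.

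A reader might infer more than the documents support:

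- *That every postmenopausal woman is misclassified.* The sterilization route is independent of FSH, so only women who rely on the postmenopausal route are affected.
- *That all these women would be excluded.* Inclusion Criterion 9 concerns only sexually active women and can be met by any listed method.
- *That a head count can be put on it.* The documents plan about 600 screened participants but give no share of women and no share who are postmenopausal.
- *That the central laboratory has programmed a flag in IU/mL.* Nothing says so. The laboratory and operations manuals are not part of the documents.
- *That the fertility-status table will be wrong, or that raising the age limit to 65 is undermined.* The SAP does not say how fertility status is derived, and both inferences need the literal limit to have been applied in practice.

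**Conclusion.** The limit is wrong as written, at the lowest severity. The conversion to 40,000 IU/L is exact. The statement that the limit is 200 to 1600 times too high and cannot be met rests on assumed postmenopausal values of 25 to 200 IU/L. Read literally, the definition closes the postmenopausal route for all women who depend on it, with extra pregnancy tests for them and a failed Inclusion Criterion 9 for a narrower group whose size the documents do not allow one to estimate. Whether any woman was in fact misclassified cannot be told from the documents. The error is conservative, and it has no bearing on the primary analysis, power or type I error.

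**What to change.** The sponsor should confirm the intended unit and correct it in Protocol Section 10.4.1.2. The number 40 appears intended in mIU/mL, equal to IU/L, but the documents do not state this, so it needs confirmation. The corrected unit should match the one in which the laboratory reports FSH, and the eligibility checklist should carry the same unit.

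The amendment history says this section was revised in Version 2.0 for consistency with the sponsor's standard text, so it is worth checking whether that standard carries the same unit.

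The cost is a one-word correction and a check of the laboratory and site materials. No analysis, sample size or SAP text has to change.

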10.4.2 Collection of Pregnancy Information

10.4.2.1 Male Participants With Partners Who Become Pregnant

- The investigator will attempt to collect pregnancy information on any male participant's female partner who becomes pregnant while the male participant is in this trial. This applies only to male participants who receive trial intervention.
- After obtaining the necessary signed informed consent from the pregnant female partner directly, the investigator will record pregnancy information on the appropriate form and submit it to the sponsor within 24 hours of learning of the partner's pregnancy. The female partner will also be followed to determine the outcome of the pregnancy. Information on the status of the mother and child will be forwarded to the sponsor. Generally, the follow-up will be no longer than 12 weeks following the estimated delivery date. Any termination of the pregnancy will be reported regardless of fetal status (presence or absence of anomalies) or indication for the procedure.

10.4.2.2 Female Participants Who Become Pregnant

- The investigator will collect pregnancy information on any female participant who becomes pregnant while participating in this trial. Information will be recorded on the appropriate form and submitted to the sponsor within 24 hours of learning of a participant's pregnancy.
- The participant will be followed to determine the outcome of the pregnancy. The investigator will collect follow-up information on the participant and the neonate and the information will be forwarded to the sponsor. Generally, follow-up will not be required for longer than 12 weeks beyond the estimated delivery date. Any termination of pregnancy will be reported, regardless of fetal status (presence or absence of anomalies) or indication for the procedure.
- While pregnancy itself is not considered to be an AE or SAE, any pregnancy complication or elective termination of a pregnancy will be reported as an AE or SAE. A spontaneous abortion is always considered to be an SAE and will be reported as such. Any post-trial pregnancy related SAE considered reasonably related to the trial intervention by the investigator will be reported to the sponsor as described in [Section 8.3.4](#). While the investigator is not obligated to actively seek

this information in former trial participants, he or she may learn of an SAE through spontaneous reporting.

- Any female participant who becomes pregnant while participating in the trial will discontinue trial intervention and be withdrawn from the trial.

10.5 Future Biospecimen Research

Use/Analysis of DNA

- Genetic variation may impact a participant's response to IMP, susceptibility to, and severity and progression of disease. Variable response to IMP may be due to genetic determinants that impact drug absorption, distribution, metabolism, and excretion; mechanism of action of the intervention; disease etiology; and/or molecular subtype of the disease being treated. Therefore, where local regulations and IRB/IEC allow, a sample will be collected for DNA analysis from consenting participants.
- DNA samples will be used for research related to emraclidine or schizophrenia and related diseases. They may also be used to develop tests/assays including diagnostic tests related to emraclidine and/or interventions of this drug class and schizophrenia. Genetic research may consist of the analysis of one or more candidate genes or the analysis of genetic markers throughout the genome or analysis of the entire genome (as appropriate).
- The samples may be analyzed as part of a multitrial assessment of genetic factors involved in the response to emraclidine or interventions of this class to understand trial disease or related conditions.
- The results of genetic analyses may be reported in the CSR or in a separate trial summary.
- The sponsor will store the DNA samples in a secure storage space with adequate measures to protect confidentiality.
- The samples will be retained while research on emraclidine or trial treatments of this class or schizophrenia continues but no longer than 15 years or other period as per local requirements.

10.6 Liver Safety: Suggested Actions and Follow-up Assessments

10.6.1 Assessment of Elevations in Liver Test Results

Elevations in liver test results occurring during a clinical trial may result from DILI. However, since DILI is a diagnosis of exclusion, it is essential to exclude other etiologies (see [Section 10.6.4](#)) that may lead to elevated results in liver tests.

When aminotransferase (ALT or AST) levels increase to $\geq 3 \times$ ULN during a clinical trial, current US guidance ([US FDA, 2009](#)) recommends close observation and diagnostic workup for causes of hepatic injury (see [Section 10.6.4](#)) other than the IMP. The International Consensus Criteria for idiosyncratic DILI only uses ALT to define DILI when referring to aminotransferase levels ([Watkins, 2019](#)). The CIOMS Working Group on DILI suggests using serum ALT as it is more specific than AST to detect and monitor the liver injury, irrespective of the cause ([EASL, 2019](#); [CIOMS, 2020](#); [Kwo et al, 2017](#)).

The medical monitor must be consulted when ALT levels increase to $\geq 3 \times$ ULN.

[Table 16](#) describes liver test monitoring during the close observation period of elevated liver tests during a clinical trial. Close observation is required until the elevations in liver test results return to baseline levels or normalize.

Table 16 Monitoring of Liver Tests

Result	Frequency for Repeating Liver (AST, ALT, Bilirubin [Total and Direct]) and INR Tests
If either of the following: 
• ALT $\geq 3 \times$ ULN and total bilirubin $\geq 2 \times$ ULN or INR > 1.5• ALT $\geq 3 \times$ ULN with symptoms and signs of hepatitis	Every 24 hours until laboratory abnormalities improve
If ALT $\geq 3 \times$ ULN and total bilirubin or INR are within the normal range	Every 48 to 72 hours until laboratory abnormalities improve
If the liver test abnormalities improve AND participants' symptoms improve or participants are asymptomatic	Frequency may decrease to once weekly

Abbreviations: ALT=alanine aminotransferase; AST=aspartate aminotransferase; INR=international normalized ratio; ULN=upper limit of normal.

